### Fitting Emax Model in R ####
library(rstanemax)
#load any other packages needed to run Emax model fit in parallel, for example:
library(rstudioapi)
dataset <- data[which(data$timepoint==t & data$population==p & data$response==r),]
## Emax Model Fit Using Stan ##
model_fit <- stan_emax(
  formula = resp ~ exposure, data = dataset,

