11.3.5 Analysis of Pharmacodynamics of Dihydroartemisinin

Analysis Plan for Primary Outcome

The primary outcome response variables are: temperature, serum lactate, serum glucose, acidosis, BCS, total and direct bilirubin, anemia. For each subject, values of the DHA exposure

parameters AUC_{0-12} and C_{max} values for each individual subject and treated as fixed in downstream PD analyses.

Regression methods will be used to characterize the relationship between exposure and responses, while controlling for covariates. For continuous response variables (temperature, serum lactate, serum glucose, acidosis, and anemia), linear, polynomial and E_{max} models with random effects will be considered. BCS is an ordinal scale designed to assess malarial coma in children, with possible values of 0, 1, 2, 3, 4, 5. Proportional odds mixed effects logistic regression will be used to model BCS.

Covariates will include exposure, timepoint, the interaction between exposure and timepoint, and potential confounding variables such as receipt of artesunate or artemisinin-based therapy prior to enrollment. Specific details of all models will be described in the SAP, and will include:

- The precise definition or derivation of each response variable, including potential transformations and the method for accounting for baseline values and/or associations between the baseline value and exposure
- The pre-specified covariates to be included in the model
- The procedure for choosing the covariance structure
- The alternative methods which may be considered, if model assumptions do not hold

For the analysis of the response variables included in the primary outcome, the set of p-values corresponding to tests of the effect of exposure on response at each timepoint will be adjusted using the Benjamini-Hochberg procedure to preserve the false discovery rate for the primary outcome at 0.05. The corresponding point estimates and CIs will be reported. Graphical displays of response by exposure at each timepoint will show individual measurements alongside model estimates. Individual trend plots of responses over time will also be generated for each response variable.

Analysis Plan for Secondary Outcomes

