In the above model, $\tau_k(P_i, t_i, BCS_{0,i}, X_i) = \Pr(BCS \leq k | P_i, t_i, BCS_{0,i}, X_i)$ represents the cumulative probability that BCS will be less than or equal to $k \in \{0,1,2,3,4,5\}$ given the covariates. The BCS level-specific intercept is represented by α_k , P_i is the exposure parameter value for the i th participant, t_i is the actual response measurement time post-first dose, $BCS_{0,i}$ is the baseline BCS for the i th participant, and X_i are the values for the i th participant of the additional covariates included in the model. The β_1 , β_2 , and η are model parameters associated with the above covariates. The term b_i represents a participant-specific random intercept, where it is assumed that b_i follow a normal distribution with mean zero and nonzero variance. For 24 hours and 48 hours post-first dose timepoints, t_i will be measured in hours post-first dose rounded to the nearest tenths place. For time of completion of the final planned dose of IV artesunate and time of first hospital discharge timepoints, t_i will be measured in days post-first dose rounded to the nearest tenths place.

The following pseudocode will be used to fit the proportional odds mixed effects models for BCS and to extract the p-value for the exposure model parameter.

```
/* Proportional odds model fit and output p-values */
proc glimmix data=dataset(where=(population=p and response=r));
*catvar = any categorical covariates included in the model;
*refvalues = the value(s) to be used as the reference level for categorical
covariate(s);
class catvar(ref=refvalues);
*baseresp = response at baseline;
*othercovars = any other covariates (including those specified in the class statement)
included in the model;
model resp = baseresp exposure time othercovars / dist=multinomial link=cumlogit;
random intercept;
by timepoint;
ods output Tests3=tests3;
run;
data tests3; set tests3(where=(effect='EXPOSURE')) ;
rename ProbF=pval;
run;
```

For the continuous primary outcome response variables, if model assumptions hold, Emax models will be fit for each primary outcome effect and each exposure parameter at each timepoint. The Emax model for primary outcome effect, E_i , is defined as follows:

$$E_i = E_{0,i} + \frac{E_{max} \times P_i^\gamma}{EC_{50}^\gamma + P_i^\gamma} + e_i,$$

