where E_i represents the given response outcome measure for the i th participant at the given timepoint, $E_{0,i}$ is the baseline response outcome effect for participant i , E_{max} is the maximum effect, EC_{50} is the exposure at half-maximal effect, P_i is the exposure parameter value for participant i , γ is the Hill parameter [7, 8] or slope coefficient, and e_i are the measurement errors for participant i . These measurement errors are assumed to be independent and normally distributed with mean zero and nonzero variance. E_{max} , EC_{50} , and $E_{0,i}$ may be modeled with fixed covariate effects, i.e., $E_{max} \sim X_i$ where X_i are the subset of covariates included for E_{max} . The subset of covariates included may differ between E_{max} , EC_{50} , and $E_{0,i}$. Alternatively, E_{max} , EC_{50} , and $E_{0,i}$ may be considered random effects if fixed effects are not included. For example, $E_{0,i}$ may also be modeled instead with a random effect, whereby an additive random component with mean-zero normal distribution will be assumed for $E_{0,i}$ such that $E_{0,i} = E_0 + b_{1i}$, where E_0 , is the population-level quantity and b_{1i} are independently normally distributed random effects with mean zero and nonzero variance. Model selection will proceed in a forward direction from least complex model (no fixed covariates included on any of the above parameters) to more complex. Estimated log-likelihood statistics or other convergence criteria will be used to assist in Emax model selection.

If Emax models are fit for a primary outcome effect, the following pseudocode will be used for model fitting and to extract p-values for the exposure model parameter

```

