## Mean and Standard Deviation of EC50, for example ##
mean(fit_param$ec50)
sd(fit_param$ec50)
```

Exploratory scatterplots for the response outcome measure at each timepoint given the exposure measure will be utilized to assess whether a log-transformation of the response variable may be necessary. These exploratory scatterplots as well as goodness of fit diagnostic plots will be used to assess reasonableness of model assumptions. If Emax model assumptions seem unlikely to hold, linear or polynomial models will be considered as informed by the exploratory scatterplots.

A linear model for primary outcome effect, E_i , is defined as follows:

$$E_i = E_{0,i} + \beta P_i + \eta^T X_i + e_i,$$

where E_i represents the given response outcome measure for the i th participant at the given timepoint, $E_{0,i}$ is the baseline response outcome measure for participant i , P_i is the exposure parameter value for participant i , X_i are the values of the additional covariates included in the model, and e_i are the measurement errors for participant i . These measurement errors are assumed to be independent and normally distributed with mean zero and nonzero variance. In addition to the covariates listed in Section 6.4, actual time of response measurement post-first dose will also be considered for inclusion in the model.

If linear models are fit for a primary outcome effect, the following pseudocode will be used for model fitting and to extract p-values for the exposure model parameter.

```
/* Linear model fit and output p-values */
proc glm data=dataset(where=(population=p and response=r));
*catvar = any categorical covariates included in the model;
*refvalues = the value(s) to be used as the reference level for categorical
covariate(s);
class catvar(ref=refvalues);
*baseresp = response at baseline;
*othercovars = any other covariates (including those specified in the class statement)
included in the model;
model resp = baseresp exposure othercovars / noint ss3;
by timepoint;
ods output ModelAnova=tests3;
run;
data tests3; set tests3(where=(source='EXPOSURE')) ;
rename ProbF=pval;
run;
```

A polynomial model for primary outcome effect, E_i , is defined as follows:

$$E_i = E_{0,i} + \sum_{j=1}^a \beta_j P_i^j + \eta^T X_i + e_i,$$

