If Emax models with no fixed covariates, linear models, or polynomial models are fit, this figure will have two panels with labels “PD Analysis Population (N=X)” and “PD Analysis Population, No Prior IV Artesunate or Other Artemisinin-Based Therapy Subset (N=X)”. If Emax models with fixed covariates on any of the model parameters are fit, then there will be one curve for every combination of fixed covariate levels for each population or subset. These may be displayed in separate panels to facilitate readability, with at most one panel per covariate level combination. For example, if an Emax model is fit with the Emax parameter fit on fixed covariates of sex and weight, the figure could have up to 8 panels with labels “Males <20 kg - PD Analysis Population (N=X)”, “Males <20 kg - PD Analysis Population, No Prior IV Artesunate or Other Artemisinin-Based Therapy Subset (N=X)”, etc.

[figure not shown]
If an Emax model is fit for the given response, exposure, and timepoint, similar plots will be displayed with actual values plotted as points and predicted values plotted as a curve for each combination of fixed covariate levels. The fitted model with estimates of Emax, EC50, E0, and the Hill parameter for each grouping of fixed covariates and analysis population or subset will be displayed in the corresponding panel.

Units will be added to all axes. At minimum, the fitted line given below the plot will have covariates for exposure, but may also have sex, weight group, receipt of IV artesunate or other artemisinin-based therapy before enrollment, receipt of concomitant medications, and actual time of measurement included as covariates. The footnote will be updated to reflect which covariates are included.

Note that models for the No Prior IV Artesunate or Other Artemisinin-Based Therapy Subset will be of the same form as that for the PD Analysis Population, but will only include the subset of covariates included in the model for the PD Analysis Population with effects that remain estimable in the No Prior IV Artesunate or Other Artemisinin-Based Therapy Subset. The footnote will be updated to only include the covariates included in the model.]

$$y=44.5-0.0061x-0.159t-0.273s+0.554w-0.139p-0.0397c$$

$$y=35.3+0.00947x-0.0994t-0.0643s+0.381w-0.0851c$$

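### The SAP never says that a child's measured baseline enters the Emax model, the first choice for the continuous primary markers, although the code for the other primary models includes it

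*SAP*

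**What the plan says.** **Order of models.** SAP Section 8.1: "For the continuous primary outcome response variables, if model assumptions hold, Emax models will be fit for each primary outcome effect". The fallback is: "If Emax model assumptions seem unlikely to hold, linear or polynomial models will be considered as informed by the exploratory scatterplots".

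**Emax equation.** The response "represents the given response outcome measure for the i th participant at the given timepoint", so it is the raw value and not a change from baseline. E_0,i "is the baseline response outcome effect for participant" i. The same paragraph then lets E_0,i be modelled with covariates, or as a population E0 plus a normal random effect. Selection moves forward from a model with no covariates on any parameter.

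**Emax code.** The model statement is "formula = resp ~ exposure, data = dataset". An optional argument offers covariate slots on Emax, EC50 and E0, and the last is a placeholder named `covar_e0`. No baseline variable is named. The note to Figure 35 promises "The fitted model with estimates of Emax, EC50, E0, and the Hill parameter" for each covariate grouping.

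**Other primary models.** The linear code reads "model resp = baseresp exposure othercovars". The polynomial and Blantyre Coma Score code contain `baseresp` as well.

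**Protocol.** Section 11.3.5 says the SAP will give "the method for accounting for baseline values and/or associations between the baseline value and exposure". SAP Section 15, which records departures from the Protocol, mentions no decision to leave baseline out of the Emax models.

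**The concern.** E_0,i has two meanings in one paragraph: a value measured on each child, and a parameter to be estimated. The code implements the second. A programmer who follows the SAP as written would get Emax fits without the child's baseline and linear or polynomial fits with it. Adjustment would then follow from the choice of curve, which is made after looking at scatterplots and fit diagnostics.

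Every child receives weight-based standard dosing, so differences in DHA exposure are observational. If sicker children have systematically higher or lower exposure, and a marker at baseline predicts the same marker later, an unadjusted exposure-response curve carries that association. Even without it, leaving out a strong predictor adds residual noise.

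**Working it through.** **1. Comparison of the four code blocks in SAP Section 8.1**

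| Model | Measured baseline in the code? |
|---|---|
| Proportional odds (BCS) | Yes, `baseresp` |
| Emax | No; unassigned `covar_e0` slot |
| Linear | Yes, `baseresp` |
| Polynomial | Yes, `baseresp` |

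The covariates in Section 6.4 that could fill the slot are sex, weight group, prior artemisinin therapy, antimalarial concomitant medication and oral ACT. The Figure 35 note describes one curve per combination of covariate levels, which suits categorical covariates and not a continuous baseline.

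**2. Reach.** The SAP counts 11 × 4 × 4 = 176 tests. Leaving out BCS, 10 × 4 × 4 = 160 are on continuous markers and so are candidates for Emax. How many will be fitted that way is not known in advance.

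**3. The random effect does not replace baseline.** The Emax data set is cut to one timepoint and one response, which leaves one record per child. With E_0,i = E0 + b_i, the variance around the curve is Var(b_i) + Var(e_i). Only the sum can be estimated, and no measured baseline enters.

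**4. The plan's own figure.** SAP Table 3 gives average power 0.85 for 176 tests, R² = 0.2, 5% non-null and N=75. Simulating simple linear regressions with Benjamini-Hochberg at 0.05 gives 0.852, so the figure reproduces.

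**5. False positives, linear-slope illustration.** Assumptions not in the documents: r is the exposure-baseline correlation, ρ the baseline-response correlation, and exposure has no effect. The unadjusted exposure-response correlation is then r × ρ. By Fisher's transformation, with δ = atanh(rρ) × √(N − 3) and √72 = 8.485, the rejection rate is Φ(δ − 1.96) + Φ(−δ − 1.96).

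| r | ρ | rρ | δ | Unadjusted rejection |
|---|---|---|---|---|
| 0.1 | 0.4 | 0.040 | 0.340 | 0.063 |
| 0.1 | 0.75 | 0.075 | 0.638 | 0.098 |
| 0.2 | 0.4 | 0.080 | 0.680 | 0.105 |
| 0.2 | 0.75 | 0.150 | 1.282 | 0.250 |
| 0.3 | 0.4 | 0.120 | 1.023 | 0.176 |
| 0.3 | 0.75 | 0.225 | 1.942 | 0.493 |

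Simulation agrees with these values to within about half a percentage point and gives about 0.05 in every cell once baseline is in the model. A further simulation tested an Emax curve with Hill coefficient 1 against a flat response. At N=75, over four correlation pairs in the r = 0.2 to 0.3 range, it rejected in 10% to 48% of runs unadjusted and 4% to 5% adjusted.

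**6. Precision, with exposure unrelated to baseline.** Suppose exposure explains 20% of the variance left after baseline. Without baseline its R² is 0.2 × (1 − ρ²). Average power at N=75, with 176 tests and 5% non-null:

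| ρ | R² without baseline | Power without | Power with |
|---|---|---|---|
| 0.3 | 0.182 | 0.79 | about 0.85 |
| 0.5 | 0.150 | 0.62 | about 0.85 |
| 0.7 | 0.102 | 0.32 | about 0.85 |

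**The case against.** **The slot on E0 could carry baseline.** This is correct as far as it goes. It would be wrong to say that the code allows nothing but exposure, or that the SAP rules baseline out. `covar_e0` is a placeholder, much like the generic covariate names in the SAS blocks. But the SAS blocks name `baseresp` separately from their generic covariates, and the Emax block does not. The SAP assigns baseline to the slot nowhere, and the starting model leaves it empty.

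**Section 6.4 and Table 19 omit baseline for every model.** This stands. A reader might take their silence as proof that Emax alone is unadjusted. It is not, because the linear and polynomial models, whose code includes baseline, are missing it from the same lists, and the sample fitted lines under Figures 35 to 38 have no baseline term either. The point rests on the Emax text and code.

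**The error rates do not describe the planned test.** This also stands. The SAP tests EC50 = 0 for Emax models and declares significance by Benjamini-Hochberg over the primary set. The rates above are per test at 0.05, from a slope or from a comparison of an Emax curve with a flat one. The 49% needs both assumed correlations at the top of their ranges.

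**Baseline may itself be post-treatment.** SAP Section 3.3 allows a value taken after the first dose when no earlier one exists. Enrolment may come up to 24 hours after the first dose, and the 24-hour response is the latest value before 24 hours. For some children the two could be the same measurement. This is a real complication, but the linear models share it. It calls for a rule, not for leaving baseline out.

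**The study is exploratory, and Table 19 will show each model's covariates.** Both are true. Disclosure after fitting does not make adjusted and unadjusted results comparable within one family of tests.

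**Conclusion.** The point holds. As written, the SAP leads to Emax fits that do not use the measured baseline, whereas the other three primary model types use it in their code, and the method that the Protocol promised is not stated for the first-choice model. This should be settled before the primary analysis is run.

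The size cannot be fixed from the documents. At N=75, with ρ between 0.4 and 0.75, the linear illustration gives per-test rejection of about 6% to 10% at r = 0.1 and about 11% to 49% at r = 0.2 to 0.3, against about 5% with adjustment. If baseline and exposure are unrelated there is no such bias, only a loss of precision that grows with ρ.

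Two stronger inferences are not supported. The first is that the primary analysis has a false-positive rate of 11% to 49%: the correlations are assumed, the planned Emax test is a different one, and the number of Emax fits is unknown. The second is that the power figures in Table 3 are wrong: they reproduce for what they describe, simple linear relationships with R² = 0.2 and no baseline term.

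**What to change.** 1. Enter the measured baseline as a continuous term on E0 in every Emax model, for example E_i = E0 + θB_i + Emax·P_i^γ/(EC50^γ + P_i^γ) + e_i, where B_i is the measured baseline. Use a fitting routine that accepts a continuous covariate, and use separate symbols for the measured baseline and the estimated E0.
2. Drop the random effect on E_0,i.
3. List the baseline value in Section 6.4, in the Table 19 covariates and in the figure equations for all model types.
4. Where the Section 3.3 baseline was taken after the first dose, do not let one measurement serve as both baseline and response. Add a sensitivity analysis restricted to children with a pre-dose baseline.

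The cost is SAP wording and code, one extra parameter per Emax model, and possibly a change of fitting software. No new data are needed, because baseline is already collected. Some children may drop out of the 24-hour analysis under item 4, and their number should be reported.

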  # include param.cov if any parameter is fitted on named fixed covariate(s)
  # omit parameter arguments from param.cov if being treated as random
  param.cov = list(emax = "covar_emax", ec50= "covar_ec50", e0 = "covar_e0"),
  # cores option included to run in parallel
  # chains will be set to a constant low integer (1, 2, or 3) multiple of the number of
  # cores, which will be the same for all Emax models fit (e.g., chains = 8)
  chains = XX, iter = 2000, cores = parallel::detectCores(logical=FALSE), seed = SEED#
)
print(model_fit)

## Extract Posterior Draws of Model Parameters ##
fit_param <- extract_param(model_fit)

## Mean and Standard Deviation of EC50, for example ##
mean(fit_param$ec50)
sd(fit_param$ec50)
```

Exploratory scatterplots for the response outcome measure at each timepoint given the exposure measure will be utilized to assess whether a log-transformation of the response variable may be necessary. These exploratory scatterplots as well as goodness of fit diagnostic plots will be used to assess reasonableness of model assumptions. If Emax model assumptions seem unlikely to hold, linear or polynomial models will be considered as informed by the exploratory scatterplots.

A linear model for primary outcome effect, E_i , is defined as follows:

$$E_i = E_{0,i} + \beta P_i + \eta^T X_i + e_i,$$

where E_i represents the given response outcome measure for the i th participant at the given timepoint, $E_{0,i}$ is the baseline response outcome measure for participant i , P_i is the exposure parameter value for participant i , X_i are the values of the additional covariates included in the model, and e_i are the measurement errors for participant i . These measurement errors are assumed to be independent and normally distributed with mean zero and nonzero variance. In addition to the covariates listed in Section 6.4, actual time of response measurement post-first dose will also be considered for inclusion in the model.

If linear models are fit for a primary outcome effect, the following pseudocode will be used for model fitting and to extract p-values for the exposure model parameter.

```
/* Linear model fit and output p-values */
proc glm data=dataset(where=(population=p and response=r));
*catvar = any categorical covariates included in the model;
*refvalues = the value(s) to be used as the reference level for categorical
covariate(s);
class catvar(ref=refvalues);
*baseresp = response at baseline;
*othercovars = any other covariates (including those specified in the class statement)
included in the model;
model resp = baseresp exposure othercovars / noint ss3;
by timepoint;
ods output ModelAnova=tests3;
run;
data tests3; set tests3(where=(source='EXPOSURE')) ;
rename ProbF=pval;
run;
```

A polynomial model for primary outcome effect, E_i , is defined as follows:

$$E_i = E_{0,i} + \sum_{j=1}^a \beta_j P_i^j + \eta^T X_i + e_i,$$

where E_i represents the given response outcome measure for the i th participant at the given timepoint, $E_{0,i}$ is the baseline response outcome measure for participant i , P_i is the exposure parameter value for participant i , a is the highest order exponent included in the model with its selection informed by exploratory data plots, X_i are the values of the additional covariates included in the model, and e_i are the measurement errors for participant i . These measurement errors are assumed to be independent and normally distributed with mean zero and nonzero variance. Again, in addition to the covariates listed in Section 6.4, actual time of response measurement post-first dose will also be considered for inclusion in the model. Estimated log-likelihood statistics or other model fit statistics may be used to assist in covariate selection for linear or polynomial models.

If linear models are fit for a primary outcome effect, the following pseudocode will be used for model fitting and to extract p-values for the exposure model parameter.

```
/* Polynomial model fit and output p-values */
data dataset; set dataset;
```

```

*exposure^j from 2 up to a will be calculated;
exposurea=exposure**a;
exposurea_1=exposure** (a-1);...
run;
proc glm data=dataset(where=(population=p and response=r));
*catvar = any categorical covariates included in the model;
*refvalues = the value(s) to be used as the reference level for categorical
covariate(s);
class catvar(ref=refvalues);
*exposure... exposurea: exposure raised to the powers 1 up to a will be included as
covariates in the model;
*baseresp = response at baseline;
*othercovars = any other covariates (including those specified in the class statement)
included in the model;
model resp = baseresp exposure... exposurea othercovars / noint ss3;
by timepoint;
ods output ModelAnova=tests3;
run;
data tests3; set tests3(where=(source='exposurea'));
rename ProbF=pval;
run;

```

Model assumptions, including normality of participant-specific measurement errors, will be assessed via exploratory scatterplots and residual plots, which will also inform whether a log-transformation of the response variable may be necessary. In the event that model assumptions are not met, additional models or transformations of the response variables will be assessed, and any changes from the analyses described in this SAP will be fully described in the interim CSR.

Models fit for the sensitivity analysis of the primary analysis using the subset of the PD Analysis Population who did not receive IV artesunate or other artemisinin-based therapy before enrollment will be of the same form as those fit in the primary analysis for the respective PD response variable, exposure parameter, and timepoint. Covariates included in each model fit for this sensitivity analysis will be those included in the respective primary analysis model with effects that remain estimable in the sensitivity analysis subset. The type of model, covariates included, and any transformations applied to the response outcome measure for each final primary analysis model will be presented in [Table 19](#) by marker of physiological dysfunction, PK exposure parameter, and timepoint for the PD Analysis Population and the subset of the PD Analysis Population that did not receive IV artesunate or other artemisinin-based therapy before enrollment.

For each model fit, the relationship between the response outcome measure at the given timepoint and the exposure measure will be assessed via a hypothesis test. If an Emax model is fit for the response outcome measure and exposure parameter, the following null hypothesis will be tested:

$$H_0: EC_{50} = 0.$$

Post-hoc distributional assessments will be performed for EC_{50} , and EC_{50} will be transformed if necessary to have an approximately normal distribution for inference. Possible transformations may include log-transformations. Point estimates and CIs for EC_{50} will be presented after their transformation back to their original scale. If any transformation is applied for the EC_{50} , the transformation will be presented in [Table 19](#).

Otherwise, if a linear model is fit for the response outcome measure and exposure parameter, the following null hypothesis will be tested:

$$H_0: \beta = 0.$$

Furthermore, if a polynomial model is fit for the response outcome measure and exposure parameter, then the following null hypothesis will be tested:

$$H_0: \beta_a = 0.$$

To adjust for multiple testing, the set of p-values for the exposure effect parameters, which correspond to tests of the effect of exposure on response at each timepoint, will be adjusted using the Benjamini-Hochberg procedure to preserve the false discovery rate for the primary outcome at 0.05 in both the primary analysis and the sensitivity analysis of the primary outcome measures. The corresponding point estimates of the parameters being tested will be presented with 95% CIs and p-values for each marker of physiological dysfunction and exposure parameter in [Table 17](#) for participants in the PD Analysis Population and in [Table 18](#) for the subset of the PD Analysis Population with no IV artesunate or other artemisinin-based therapy before enrollment. Significant p-values after the Benjamini-Hochberg procedure has been performed will be indicated.

Individual trend plots for each marker of physiological dysfunction over time will be presented by sex and weight group beginning in [Figure 24](#) and continuing through [Figure 34](#). Graphical displays of each marker of physiological dysfunction by exposure will be presented by planned timepoint beginning in [Figure 35](#) and continuing through [Figure 210](#) for participants in the PD Analysis population and in the subset of the PD Analysis Population that did not receive any IV artesunate or other artemisinin-based therapy before enrollment. These figures will show individual measurements alongside model estimates.

Individual listings of BCS assessments will be presented in [Listing 11](#). Individual listings of temperature are included in [Listing 20](#). Individual listings of biochemistry and hematology markers of physiological dysfunction are given in [Listing 17](#) and [Listing 18](#), respectively. Individual listings of exposure parameters by weight group will be presented in [Listing 13](#).

